3 STUDY OBJECTIVE(S) AND DESIGN

3.1 Study Objective(s)

The objectives of this study are to verify the superiority of ASP015K alone or in combination with DMARDs over placebo in terms of efficacy, at doses of 100 mg/day and 150 mg/day, in patients with rheumatoid arthritis (RA) who had an inadequate response to DMARDs, as measured by the ACR20 response rate at Week 12, which is the primary variable; to evaluate the pharmacokinetics, pharmacodynamics, and safety of ASP015K; and to evaluate the efficacy and safety of long-term treatment with ASP015K (52 weeks).

3.2 Study Design

This is a Japanese, Korean and Taiwanese, multi-center, randomized, placebo-controlled, double-blind, parallel-group, confirmatory study to evaluate the efficacy and safety of ASP015K alone or in combination with DMARDs, at doses of 100 mg/day and 150 mg/day, in patients with RA who had an inadequate response to DMARDs. Open-label etanercept will also be administered as the reference drug for 52 weeks (the last dose will be given at Week 51). In the study, ASP015K (test drug) and placebo (comparative drug) will be given as study drugs, and etanercept will be given as a separate reference drug. DMARD response is evaluated at the initiation of screening and then after the screening period, subjects will be randomized in a 1:1:1:2 ratio to the ASP015K 100 mg, ASP015K 150 mg, placebo, or reference groups, and they will receive either the study drug or reference drug for 52 weeks. Subjects in the ASP015K 100 mg, ASP015K 150 mg, and placebo groups will orally receive either ASP015K or placebo once daily after breakfast, while those in the reference group will receive 50 mg of subcutaneous etanercept once weekly.

The planned sample size is 100 subjects each for the ASP015K 100 mg, ASP015K 150 mg, and placebo groups and 200 subjects for the reference group.

Re-screening is allowed only in situations in which a subject underwent the screening procedures (i.e., scans and laboratory work) and owing to logistical circumstances, the allocated time window for these tests has expired. Re-screening is not permitted in cases in which the initial test results do not support eligibility based on inclusion and exclusion criteria. The subject must be classified as a screening failure at that time point.

Based on the consideration of the ethical issues related to long-term placebo use, at Week 12 subjects in the placebo group will be switched to either ASP015K 100 mg or ASP015K 150 mg, and the dosage will be maintained until the end of treatment. The ASP015K dose that will be started for placebo group subjects at Week 12 (100 or 150 mg) will be randomly chosen at baseline. The dose will be switched under the blinded condition.

Subjects in the ASP015K 100 mg, ASP015K 150 mg, or placebo groups who complete this study will be eligible for participation in the open-label extension study (015K-CL-RAJ2). Subjects will make a follow-up visit after the Week 52 visit if they do not enroll into the extension study on the day of the Week 52 visit.

Safety data obtained from this study will be reviewed by the Independent Data and Safety Monitoring Board (DSMB), which will make recommendations on study continuation, termination, or protocol revision from the safety perspective.

3.3 Randomization

The person responsible for assigning study drugs will randomly assign the study drugs and retain the treatment code under secrecy until the breaking of the treatment code.

The Case Registration Center will assign subjects who have been found to be eligible for enrollment in accordance with the case registration procedures to 1 of the following groups: ASP015K 100 mg, ASP015K 150 mg, placebo, or reference groups at baseline in 1:1:1:2 ratio. At Week 12, subjects in the placebo group will be switched to receive either ASP015K at a dose of 100 mg or ASP015K at a dose of 150 mg. The dose of ASP015K (100 mg or 150 mg) to be administered to the placebo group from Week 12 will be determined in advance randomly at baseline, and study drugs must be switched under double-blind conditions.

To minimize potential bias in this study, dynamic allocation procedures in each study region (Japan, Korea, and Taiwan) will be used by biased-coin minimization with the following 1 to 3 as factors:

1. Study center;
2. Prior Biologic DMARD-IR at baseline; and
3. Concomitant DMARD at Baseline use at the initiation of treatment with the study drug or reference drug.

All drug numbers are assigned randomly by the Case Registration Center under blind conditions.

4 SAMPLE SIZE

One hundred subjects per group will receive the study drug and 200 subjects the reference drug (a total of 500 subjects).

[Rationale for the sample size]

Based on 015K-CL-RAJ1 result and efficacy result from other RA drugs [XELJANZ[®], tablet, 5 mg, CTD (2013)] [CIMZIA, sc, 200 mg, Syringe, CTD (2012)], 62 subjects per group will provide 90% power to detect a difference assumed in the Step 2 in the closed testing procedure (described in Section 7.4.1.1 Primary Analysis) under the following assumptions. In addition, it is assumed that ACR20 response rate of each country (Japan, Korea and Taiwan) is similar.

- ACR20 response rate at Week 12 in the placebo group: 25%
- ACR20 response rate at Week 12 in the ASP015K 100 mg group: 54.5%

- ACR20 response rate at Week 12 in the ASP015K 150 mg group: 65.5%
- Two-sided significance level of 0.05

On the other hand, according to the Extent of Population Exposure to Assess Clinical Safety for Drugs Intended for Long-term Treatment of Non-life-threatening Conditions (PAB/PCD Notification No.592, dated 24 May 1995), ("the long-term treatment guideline"), a sample size of 300-600 subjects under long-term treatment (6 months) is adequate to observe delayed adverse events at a reasonable frequency (generally, 0.5% to 5%) and to observe whether there is an increase in high-frequency adverse events during the later stage of treatment. For treatment lasting 1 year, 100 subjects is acceptable. It is also described in "Guidelines on methodology for clinical assessment of antirheumatic drugs" (PFSB/ELD Notification No. 0217001, dated 17 February 2006) that 100 subjects for 1 year are necessary.

Therefore, to collect data for 300 subjects for 6 month period, and for 100 subjects for 1 year period in both ASP015K 100 mg and 150 mg groups among 015K-CL-RAJ2/RAJ3/RAJ4 studies as long-term treatment data, approximately 80 subjects per treatment group (400 subjects in total) as a target are necessary to be enrolled in Japan. In addition, the target sample size for Taiwan is set at 10 subjects per treatment group (50 subjects in total) as a target in consideration of the requirement of regulatory authority in Taiwan (10% or more Taiwan subjects) and target sample size for Korea is also set at 10 subjects per treatment group (50 subjects in total) as a target. Therefore, the target sample size per treatment group is set at 100 subjects in total for 3 regions.

[Rationale for the sample size for the reference group]

The target sample size for the reference group was set at 200 subjects, considering the followings:

- Incidence rates for serious infections from post marketing studies for approved biologic drugs: approximately 1.0% to 3.6% reported in post-marketing all-case surveillance [ACTEMRA[®], drip infusion, 80 mg, 200 mg, 400 mg, final reports for all patients] [ORENCIA[®], drip infusion, 250 mg, information for appropriate drug usage] [HYUMIRA[®], sc, 40 mg, Syringe 0.8 mL, information for appropriate drug usage]; and approximately 2.4% in the 5 mg group and approximately 1.5% in the Adalimumab group, as revealed by pooled analysis of the phase III tofacitinib study [XELJANZ[®], tablet, 5 mg, CTD (2013)]
- Operational feasibility

Setting the sample size of reference group as 200, it can be detectable at least 1 subject with 95% confidence probability for AE which occurs at 1.5% incidence rate.

5 ANALYSIS SETS

In accordance with International Conference on Harmonization (ICH) recommendations in guidelines E3 and E9, the following analysis sets will be used for the analyses. FAS will be the primary data set for efficacy analyses.

5.1 Full Analysis Set (FAS)

FAS will consist of all subjects who are randomized and receive at least 1 dose of the study drug or reference drug. This will be the primary data set for efficacy analyses.

5.2 Per Protocol Set (PPS)

PPS includes all subjects of FAS who meet the following criteria. PPS is defined based on the data up to Week 12.

- Have no violation of inclusion criteria;
- Do not meet any exclusion criteria possibly interfering with the efficacy evaluation;
- Receive study or reference treatment for 8 weeks (56 days) or longer from the initiation of treatment to Week 12* (those who have discontinued the study drug or reference drug due to the lack of efficacy should be included in PPS);
- Have study or reference treatment compliance of 75% or higher for 12 weeks after treatment;
- Have evaluable primary efficacy variables; and
- Have no major protocol violations after registration.

Subjects who are considered to have no impact on the efficacy evaluation at the Case Review Meeting will also be included in PPS, if they are not satisfying these criteria.

*: The duration of treatment with the study drug will be calculated by subtracting the first day of study drug treatment from the date of treatment completion plus 1 day, and the duration of treatment with the reference drug will be calculated by subtracting the first day of reference drug treatment from the date of treatment completion plus 8 days.

5.3 Safety Analysis Set (SAF)

SAF is defined as all subjects who received at least 1 dose of the study drug or reference drug.

5.4 Pharmacokinetic Analysis Set (PKAS)

PKAS will consist of all subjects who receive at least 1 dose of the study drug and who provide samples for drug concentrations for at least 1 time point.

5.5 Pharmacodynamic Analysis Set (PDAS)

All subjects who receive at least 1 dose of the study drug or 1 injection of the reference drug and who provide samples for the determination of pharmacodynamic parameters at least 1 time point will be included in PDAS.

6 ANALYSIS VARIABLES

6.1 Efficacy Endpoints

6.1.1 Primary Efficacy Endpoints

- ACR20 response rate at Week 12 or early termination (Week 12/ET)

Definitions

ACR20 response rate at Week 12 or early termination (Week 12/ET)

It is defined as percentage of subjects achieving ACR 20 response at Week 12/ET, based on C-reactive protein (CRP). ACR20 is a binary variable, with levels responder and non-responder.

Responder :

A subject will be defined as an ACR20-CRP responder at any time point (e.g. Week 12/ET) if the subject meet ALL the following American College of Rheumatology (ACR) response criteria:

- At least 20% reduction from baseline at the time point (e.g. Week 12/ET) in the number of 68 tender joint count (TJC-68)

AND

- At least 20% reduction from baseline at the time point (e.g. Week 12/ET) in the number of 66 swollen joint count (SJC-66)

AND

- At least 20% reduction from baseline at the time point (e.g. Week 12/ET) in ANY 3 or more of the 5 following ACR components
 - Subject's global assessment of arthritis pain (SGAP) (assessed using a 100 mm VAS ; score of 0 indicates no pain, and score of 100 indicates very severe pain)
 - Subject's global assessment of arthritis (SGA) (assessed using a 100 mm VAS; score of 0 indicates no disease activity, and score of 100 mm indicates very severe disease activity)
 - Physician's global assessment of arthritis (PGA) (assessed using a 100 mm VAS; score of 0 indicates no disease activity, and score of 100 mm indicates very severe disease activity)

- Health Assessment Questionnaire – Disease Index (HAQ-DI; score ranges from 0 to 3 with higher scores indicating greater disability)
- CRP (Higher values indicate greater inflammation)

Baseline is defined in Section 7.11.4. A negative percent change indicates a reduction from baseline (i.e., a favorable outcome). If the baseline value is 0 in some of ACR components, then that component is regarded as non-responder at that component and used for ACR calculation. The handling of missing data in ACR components is described at Section 7.11.2.

Non-responder: A subject will be defined as an ACR20-CRP non-responder at the time point (e.g. Week 12/ET), if the subject does not meet the ACR20-CRP responder criteria.

6.1.2 Secondary Efficacy Variables

6.1.2.1 Categorical Variables

Categorical efficacy variables are:

- Percentage of subjects achieving ACR 20/50/70-CRP response at each analysis visit (except ACR20 Week 12/ET)
- Percentage of subjects achieving ACR 20/50/70-ESR response at Week 12/ET

Note: ACR 20-ESR response is similar to definition in 6.1.1 by replacing CRP with ESR.

- Percentage of subjects achieving ACR20-CRP response at Week 4 and sustaining the response at Weeks 8 and 12
- Percentage of subjects achieving ACR20-CRP response at Week 8 and sustaining the response at Week 12

Calculation DAS-CRP/ESR response:

DAS-CRP/ESR response is consist of following parameters, and calculated according to below description.

- TJC (28 joints)
- SJC (28 joints)
- CRP or ESR
- SGA

[When CRP is used]

$$\text{DAS28} = 0.56\sqrt{\text{TJC}} + 0.28\sqrt{\text{SJC}} + 0.36 \ln(\text{CRP} + 1) + 0.014 \times \text{SGA} + 0.96$$

[When ESR is used]

$$\text{DAS28} = 0.56\sqrt{\text{TJC}} + 0.28\sqrt{\text{SJC}} + 0.70 \ln \text{ESR} + 0.014 \times \text{SGA}$$

Note: CRP values measured in mg/dL will be converted to mg/L for analysis purposes as: value in mg/L = value in mg/dL × 10; SGA is measured on 100 mm VAS. If any component is a missing value, then DAS28-CRP/ESR will be a missing value. If ESR is 0 then DAS28-ESR is missing.

- Percentage of subjects achieving DAS28-CRP score <2.6 at each analysis visit
- Percentage of subjects achieving DAS28-ESR score <2.6 at each analysis visit
- Percentage of subjects achieving DAS28-CRP score ≤3.2 at each analysis visit
- Percentage of subjects achieving DAS28-ESR score ≤3.2 at each analysis visit

Table 2 Definition EULAR

DAS28 after treatment	DAS28 improvement (DAS28 before treatment - DAS28 after treatment)		
	> 1.2	> 0.6 and ≤ 1.2	≤ 0.6
≤ 3.2	Good response	Moderate response	No response
> 3.2 and ≤ 5.1	Moderate response	Moderate response	No response
> 5.1	Moderate response	No response	No response

Note: If DAS28 score is missing at baseline, then post-baseline DAS28 improvement score will not be calculated and DAS28 EULAR response will be a missing value.

- Percentage of subjects in DAS28-CRP EULAR response criterion of "Good Response" at each analysis visit
- Percentage of subjects in DAS28-ESR EULAR response criterion of "Good Response" at each analysis visit
- Percentage of subjects in DAS28-CRP EULAR response criterion of "Good Response" or "Moderate Response" at each analysis visit
- Percentage of subjects in DAS28-ESR EULAR response criterion of "Good Response" or "Moderate Response" at each analysis visit
- Percentage of subjects achieving ACR/EULAR score for remission at each analysis visit
If all of the following 4 parameters are fulfilled, it is defined as remission:
 - TJC (68 joints) ≤ 1
 - SJC (66 joints) ≤ 1
 - CRP ≤ 1 mg/dL
 - SGA ≤ 1 cm (on a VAS of 0-100 mm).

Note: All 4 conditions must be fulfilled to be in remission. If any component is a missing value, then ACR/EULAR score for remission will be a missing value.

- Percentage of subjects with a SDAI score of ≤3.3 at each analysis visit
SDAI score is consist of following parameters, and calculated according to below description.
 - TJC (28 joints)
 - SJC (28 joints)
 - SGA (0-10 cm VAS)

- PGA (0-10 cm VAS)
- CRP (mg/dL)

$$\text{SDAI} = \text{TJC} + \text{SJC} + \text{SGA} + \text{PGA} + \text{CRP}$$

Note: If any component is a missing value, then SDAI score will be a missing value.
Percentage of subjects achieving HAQ-DI (≤ 0.5) at each analysis visit

- Percentage of subjects with a CDAI score of ≤ 2.8 at each analysis visit
CDAI score is consist of following parameters, and calculated according to below description.
 - TJC (28 joints)
 - SJC (28 joints)
 - SGA (0-10 cm VAS)
 - PGA (0-10 cm VAS)

$$\text{CDAI} = \text{TJC} + \text{SJC} + \text{SGA} + \text{PGA}$$

Note: If any component is a missing value, then CDAI score will be a missing value.

- Percentage of subjects achieving HAQ-DI (≤ 0.5) at each analysis visit
- Percentage of subjects achieving decrease of baseline HAQ-DI of at least 0.22 at each analysis visit
- Percentage of subjects achieving SF-36v2 of difference ≥ 5 at each analysis visit

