- CRP (mg/dL) is below measurement (i.e. <0.01 mg/dL) then CRP is regarded as 0.01 U/ml, and used for the calculation of DAS28-CRP, etc. and categorized in <1.0 mg/dL.
- Baseline for efficacy is defined as value at Day1 before the first dose of study drug or reference drug for all subjects including placebo or reference group assigned subjects.
- Change from baseline to post-baseline will be calculated as: post-baseline value - baseline value. If the baseline value is missing, then that subject is not included in the calculation at any visit.
- Percent change from baseline to post-baseline will be calculated as: $100 \times (\text{change} / \text{baseline})$. If the baseline value is 0 or missing, or post-baseline value is missing, then percent change from baseline to post-baseline is missing.
- If onset date of AE is Unknown, then missing onset date of AE will be imputed as following steps.
 1. If only the day of the month is missing (e.g., 2013-03), then the first day of the month will be used (2013-03-01),
 2. If both day and month are missing (e.g., 2013), then the first day of January will be used (2013-01-01).
 3. If imputed onset date of AE is earlier than the first date of study drug, then the onset date of AE is onset at the first date of study drug, because AE data in CRF is collected only after the first date of study drug.

- If the start date of concomitant medication is Unknown, then the missing date will be imputed as following steps.
 1. If only the day of the month is missing (e.g., 2013-03), then the first day of the month will be used (2013-03-01),
 2. If both day and month are missing (e.g., 2013), then the first day of January will be used (2013-01-01).

- If the end date of concomitant medication is Unknown, then the missing date will be imputed as following steps.
 3. If only the day of the month is missing (e.g., 2013-03), then the last day of the month will be used (2013-03-31),
 4. If both day and month are missing (e.g., 2013), then the last day of December will be used (2013-12-31).

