5	Placebo Multiple Imputation (pMI)	
<Step3>Combine Part
 
In accordance with Rubin’s rule (Little and Rubin, 2002), the 1000 estimated ACR20 response rate in each treatment groups are combined. In addition, the difference between ASP015K 100 mg and placebo, the difference between ASP015K 150 mg and placebo, the difference between Etanercept, and 95% confidence interval for the difference will be combined. Moreover, the Wald's chi-squared test using logistic regression model with treatment group (Placebo, ASP015K 100 mg, ASP015K 150 mg), the prior biologic-DMARD-IR (No, Yes), concomitant, DMARD use (No, Yes) and study region (Japan, Korea, and Taiwan) as factor will also be calculated.

For use in all DAS28 and DAS28-based analyses, unless otherwise specified in Section 10.2 Appendix 1
		
6	LOCF DAS28 CRP components	
 • LOCF all missing DAS28 CRP component value(s) and then calculate the DAS28 score.

Missing Data in HAQ-DI

For HAQ-DI, there are 20 items in 8 categories, with each category having 2 or 3 questions. A subject must have a score in ≥ 6 of the 8 categories, otherwise the HAQ-DI cannot be computed and will be considered missing for data summarization and analysis purposes. If responses to individual questions within a category are missing, they are not imputed. Therefore, the score in each category is based on non-missing responses. A category score is missing when all responses within a category are missing.

Missing Data in SF-36v2

For SF-36v2, there are 8 scales (domains). Missing values will be imputed if at least half of the items in the domain that included the missing item score(s) are non-missing. In that case, the missing value will be imputed with the average score of the non-missing item scores in this domain.

Missing Data in WPAI

For WPAI Scale Score, each score will be computed on condition that the all of the questions for each score will not be non-missing.

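### Setting DAS28-ESR to missing when ESR is 0 drops only the most favourable ESR readings and may slightly understate the DAS28-ESR results

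*SAP*

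**What the plan says.** SAP Section 6.1.2.1 defines DAS28-ESR from the 28-joint tender and swollen counts, SGA and a term of 0.70 times the natural log of ESR. The note to the formula adds: "If ESR is 0 then DAS28-ESR is missing".

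The score feeds several endpoints in the same section, among them "Percentage of subjects achieving DAS28-ESR score <2.6 at each analysis visit" and "Percentage of subjects achieving DAS28-ESR score ≤3.2 at each analysis visit". It also feeds EULAR good response, EULAR good or moderate response and, in Section 6.1.2.2, change from baseline. For EULAR response, "If DAS28 score is missing at baseline, then post-baseline DAS28 improvement score will not be calculated".

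Three other places bear on the point:

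- **Low CRP (SAP 7.1).** For a CRP below the measurement limit of 0.01 mg/dL, "then CRP is regarded as 0.01 U/ml", and the value is then used in DAS28-CRP. The printed unit differs from the mg/dL of the limit, but the intent to keep the subject is clear.
- **Imputation (SAP 7.11.2, Table 8, last row).** The row is headed as applying to all DAS28 analyses, but its instruction is to carry forward "all missing DAS28 CRP component value(s) and then calculate the DAS28 score". ESR is not named.
- **ESR itself (SAP 6.1.2.1 and 6.1.2.2).** Raw ESR and its change are analysed, and ACR20/50/70 is also computed with ESR in place of CRP. No exclusion of zeros is stated there.

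**The concern.** A recorded ESR of 0 is a result, and the most favourable one possible. Declaring the score missing ties the missingness to the quantity being measured and does so at one end of the scale only. If the affected subjects do better than their arm as a whole, leaving them out pulls the arm's DAS28-ESR results down. An arm with more zeros loses more.

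The SAP is also uneven. It substitutes a value for low CRP, where the formula uses ln(CRP + 1) and would be defined even at 0. It discards the score for ESR, where a substitute is needed. One ESR reading of 0 can count as a complete reduction in ACR20-ESR and as no data in DAS28-ESR at the same visit.

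At stake are the secondary DAS28-ESR comparisons with placebo up to Week 12, and the descriptive summaries to Week 52 that sit beside etanercept.

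**Working it through.** The plan gives no figure for this rule, so there is nothing to reproduce. The check has four steps.

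**1. Are subjects with ESR 0 likely to be in remission?** Suppose 0 is replaced by 1 mm/hr, so that 0.70 × ln(1) = 0. The score becomes 0.56√TJC + 0.28√SJC + 0.014 × SGA. The ESR term would be 1.61 at ESR 10 and 2.10 at ESR 20.

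| TJC / SJC / SGA | DAS28-ESR with ESR set to 1 | Category |
|---|---|---|
| 1 / 1 / 10 | 0.98 | remission |
| 4 / 4 / 30 | 1.12 + 0.56 + 0.42 = 2.10 | remission |
| 6 / 6 / 30 | 2.48 | remission |
| 9 / 9 / 20 | 2.80 | low disease activity |
| 16 / 9 / 60 | 3.92 | neither |

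Remission is likely even with several active joints, but it is not guaranteed. For EULAR response, the fall in ESR alone gives an improvement above 1.2 when baseline ESR exceeds exp(1.2/0.70) = 5.55, that is, 6 or more.

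**2. Direction.** Take n subjects, r true remitters and k subjects with ESR 0, of whom a share q would be in remission. After exclusion the rate is (r − kq)/(n − k). This is below r/n exactly when q > r/n, so the rate falls only if the excluded subjects remit more often than their arm average.

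**3. Size.** The planned arm size is 100 (SAP Section 4). The values of r, k and q are assumptions.

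- With r = 25 and q = 1: k = 1 gives 24/99 = 24.2%, and k = 2 gives 23/98 = 23.5%.
- With r from 10 to 40 and k from 1 to 5, the change is −0.6 to −4.7 points at q = 1, −0.1 to −2.1 at q = 0.5, and +0.1 to +2.1 at q = 0.
- Between arms, take 30% active against 10% placebo, with zeros in the active arm only and all of them remitters. The difference of 20.0 points (odds ratio 3.86) becomes 19.3 (3.73) at k = 1, 18.6 (3.60) at k = 2 and 16.3 (3.21) at k = 5.

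An illustrative simulation gives a sense of likely frequency. It assumes log-normal ESR (log-scale SD 0.9) rounded down to whole numbers, joint counts with a median near 3 and SGA centred on 30. At median ESR 15 to 25, zeros were 0.02% to 0.13% of readings and the loss in remission was about 0.01 to 0.1 point. At median ESR 5 to 8, zeros were about 1% to 3.7% and the loss was 0.5 to 1.9 points. Between 75% and 97% of the subjects with ESR 0 were in remission.

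**4. What happens to the subject?**

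- *Weeks 4, 8 and 12:* no imputation applies, so a missing score leaves the logistic and ANCOVA models.
- *Week 12/ET:* two readings are open. ESR is recorded, so no component is missing and the carry-forward in Table 8 does not start; the score is missing and the subject drops out. Alternatively, the carry-forward or the closest-date rule in Section 7.11.5 brings in an earlier ESR above 0. In the 4 / 4 / 30 example, an earlier ESR of 10 would turn 2.10 into 2.10 + 1.61 = 3.71, which loses both remission and low disease activity.
- *Baseline:* an ESR of 0 removes EULAR response and change from baseline at every later visit.

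**The case against.** The strongest reply is that the effect is small, uncertain and harmless to the trial's claim. Most of this stands.

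- **Direction.** A reader might infer that the rule lowers remission in the arm that suppresses inflammation most. The documents do not support that as a fact. They do not show that ESR 0 occurs at all, or that it is commoner in one arm, and step 2 shows that the sign depends on q. The formula makes a high q likely; the imbalance between arms is unsupported.
- **Reach.** A reader might infer that these subjects leave the efficacy analysis. They do not. They stay in ACR20-CRP, DAS28-CRP, SDAI, CDAI, ACR/EULAR remission, ESR itself and the ACR-ESR responses. The time-to-remission analysis uses DAS28-CRP.
- **Size.** A shift of 0.8 to 1.5 points is well below the standard error of a 25% rate in 100 subjects, √(0.25 × 0.75/100) = 4.3 points.
- **The CRP parallel.** It is imperfect. Low CRP is a result below an assay limit, while ESR 0 is a local reading (Protocol 5.3.1.3). To call the two DAS28 versions not comparable because of this rule would go too far, since they already differ in formula and laboratory.
- **Status.** These are secondary variables without multiplicity adjustment (SAP 7.4.2), summarised without tests after Week 12.

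What the reply does not remove is that missingness is set by the outcome, at one end of the scale, and that no other part of the SAP corrects it.

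**Conclusion.** The point holds as a minor one. The rule creates outcome-dependent missingness confined to the lowest ESR values. It may slightly understate DAS28-ESR remission, low disease activity, EULAR response and mean improvement, more so wherever ESR 0 is more frequent. The size is probably a point or less per affected subject per 100. The shift from 25.0% to 24.2% or 23.5% assumes one or two zeros, all of them remitters, in one arm. Week 12/ET handling is unsettled, though either reading tends in the same direction.

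A reader might infer that the efficacy conclusion is at risk. It is not. Primary ACR20-CRP and all DAS28-CRP analyses are untouched, and a bias of this kind against placebo would probably be conservative. The descriptive picture beside etanercept could shift either way, depending on where the zeros fall.

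**What to change.** In SAP Section 6.1.2.1, replace the sentence with: *An ESR of 0 mm/hr is replaced by 1 mm/hr (so that ln ESR = 0) before DAS28-ESR is computed.* This matches the SAP's practice of keeping low CRP values in Section 7.1. It also settles Week 12/ET for these readings, because a score then exists. Add a short table of the number of ESR 0 readings by arm and visit, so that any effect can be seen.

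The cost is one sentence and one small table. The downside is small: 0 and 1 mm/hr are treated alike, and a local reading of 0 that is really an error is kept. If the SAP can no longer be changed, the same substitution can be run as a sensitivity analysis and justified in the clinical study report, as SAP Section 1 allows.
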